1.0 PURPOSE and OBJECTIVES

The purpose of this study is to compare the safety and efficacy of clobetasol propionate .05% ointment to fractional CO2 laser procedure for the treatment of vulvar lichen sclerosis.

Primary Outcome Measures:

- The primary outcome will be the subjective and objective cure of vulvar symptoms of itching, burning, dyspareunia at 12 weeks post treatment, or 6 months [Time Frame:12 weeks] using the SkinINDEX-29 and Vulvar Symptom Visual Analog Scale (VAS)

Secondary Outcome Measures:

- Complications [Time Frame: 6 week, 6 months, 1 year] pain, infection, de novo or worsening dyspareunia, contact dermatitis and burns
- Subjective Vulvovaginal Symptoms Questionnaire (VSQ)
- Objective Cure of Lichen Sclerosus [Time Frame:6 months, 1 year] using PHOTO documentation, Vulvar Signs Visual Analog Scale
- Health Related Quality of Life (HRQOL) based on patient global impression of improvement and satisfaction as well as the Vaginal Health Index [Time Frame: 6 months, 1 year]

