5.0 SAMPLE SIZE CALCULATION

The study will consist of 2 study groups (LASER vs STEROID therapy). We expect improved subjective and objective results in the LASER group at 3 months post treatment or 6 months from enrollment compared with the STEROID group.

This study is designed as a two-group randomized clinical trial. Sample size calculations were conducted using the absolute change in the Skindex 29 as the primary end point. Our study will reach 80% power to detect a mean difference of 16 points on the Skindex 29 (sd=22 for both groups)²² between the study groups with 24 patients in each group, or 48 in total based on a one-sided two-sample t-test with alpha=0.05. By accounting for 10% attrition, we propose to recruit 52 patients to the study to be randomized with a 1:1 ratio to each group, with a blocked component for those who used topical clobetasol in the past. The Skindex-29 has validated cutoff categories for mildly, moderately, and severely impaired health related quality of life scores, the mean difference between each quality of life measure overall score is between 6 and 7. Therefore, powering the study for a detection of mean difference of 16 points should measure significant quality of life improvement.^{23,24}

Study Timeline:

	Intake Visit	Day 0	2 weeks	4 weeks-14 weeks	6 months	1 year
Vulvar biopsy (if never completed)	X					
Vaginal STEROID or LASER			STEROID daily x 4 weeks LASER monthly x 3 months	STEROID three times weekly x 8 more weeks, then as needed LASER STOP at 12 weeks		
Vaginal Health Index scale (VHIS)		X			X	x
SkIndex-29 Vulvar QoL Questionnaire Vulvovaginal Symptoms Questionnaire (VSQ)		X			X	x
Telephone call to check compliance and answer questions			X	X (8 weeks)		
Photodocumentation		X			X	x
Questionnaire of patient global impression of improvement and satisfaction PGI-I					X	x

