6.0 DATA COLLECTION and TRANSMISSION

The data will be collected from study participants at MedStar Washington Hospital Center or other Medstar Urogynecologic Clinic. All data collection will be performed by research staff. The baseline, 6 month, and 1 year visits will be in-person and include clinic evaluations. The 2 week and 2-month telephone call will be performed by the research coordinator. At screening, each subject will be assigned a subject identification. Case report forms will be generated for each subject and completed by the investigator or study coordinator. Original case report forms will be securely maintained. Data will be entered into a secure RedCAPS Database which provides complete auditing for data management processes.

De-identified backup data will be kept in locked files at the participating site. Plans for publication will be handled by the investigators at MedStar Washington Hospital Center and will adhere to publication policies.

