9.0 SOURCES OF MATERIALS

Medical record data and program records will be obtained for each participant. Demographic information and personal history will be obtained by interview. Study data, such as information obtained at follow-up assessment examination and interviews, will be obtained according to the time-frame specified in the protocol.

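### Complications are due at 6 weeks from an unstated origin, and no early contact common to both arms is assigned to collect them

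*Combined protocol and SAP*

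**What the plan says.** Section 1.0 gives the comparison of safety, alongside efficacy, as the purpose of the trial. Its secondary outcomes include "Complications [Time Frame: 6 week, 6 months, 1 year] pain, infection, de novo or worsening dyspareunia, contact dermatitis and burns". No origin is given for these times.

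The Section 5.0 timeline has columns for intake, Day 0, 2 weeks, 4 to 14 weeks, 6 months and 1 year. Its rows cover biopsy, treatment, the vaginal health index, Skindex-29 with the VSQ, telephone calls, photographs and the global impression questionnaire. The call row reads "Telephone call to check compliance and answer questions" and is marked at 2 and 8 weeks. The first treatment entry, "STEROID daily x 4 weeks LASER monthly x 3 months", stands in the 2-week column.

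Section 6.0 adds: "The 2 week and 2-month telephone call will be performed by the research coordinator". On visits it says: "The baseline, 6 month, and 1 year visits will be in-person and include clinic evaluations". On forms: "Case report forms will be generated for each subject and completed by the investigator or study coordinator". Section 3.0 gives the laser arm three clinic sessions 4 weeks apart.

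Section 8.0 promises adverse event monitoring of all participants, without times or a method, and has the safety board review serious events. Section 9.0 says "Medical record data and program records will be obtained for each participant" and "Study data, such as information obtained at follow-up assessment examination and interviews, will be obtained according to the time-frame specified in the protocol".

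**The concern.** The schedule, followed as written, does not deliver an outcome that the protocol names. Week 6 lies inside the 4 to 14 week column, but the only assessment marked there is the 8-week call, and its stated purpose does not include complications.

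The arms also differ in how often staff see the patient. Laser patients are in clinic during treatment, whereas steroid patients have no scheduled clinic visit before 6 months. Some difference is inherent in comparing a clinic procedure with an ointment used at home. The plan does not set an equal way of asking alongside it.

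At stake is the early comparison of complications. Section 2.0 itself says that little is known about the long-term effects of this laser in the vulva or vagina, and that earlier laser studies in lichen sclerosus were small and retrospective. An early complication that nobody asks about, and that no record happens to mention, cannot be restored at analysis.

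**Working it through.** The plan gives no figure on this point to reproduce. Its one design calculation, the sample size for Skindex-29, is not involved. The check sets the schedule against the possible meanings of the 6-week point.

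**Inputs.** Calls at weeks 2 and 8 (Sections 5.0 and 6.0). Visits at 6 months and 1 year, taken as weeks 26 and 52 from Day 0 (assumption). Three laser sessions 4 weeks apart (Section 3.0). A fixed steroid course of 4 + 8 = 12 weeks (Section 5.0). Treatment starting at Day 0 or at week 2; the week-2 reading rests on where the timeline places the treatment entry.

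**Laser sessions.** Day 0 start: weeks 0, 4, 8. Week-2 start: weeks 2, 6, 10.

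**Where the 6-week point falls, in weeks from Day 0.**

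| Counted from | Day 0 start | Week-2 start |
|---|---|---|
| Day 0 | 6 | 6 |
| First treatment | 0 + 6 = 6 | 2 + 6 = 8 |
| Third laser session | 8 + 6 = 14 | 10 + 6 = 16 |
| End of fixed steroid course | 12 + 6 = 18 | 14 + 6 = 20 |

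The range is week 6 to week 20. Counting from intake cannot be placed on this scale, because the gap between intake and Day 0 is not given. The contacts common to both arms are at weeks 2, 8, 26 and 52, so only one reading matches: 6 weeks after first treatment with a week-2 start, which is the 8-week call.

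**Does other text settle the origin?** A week-2 start has support. The steroid course would end at 2 + 12 = week 14, the end of the 4 to 14 week column, and 14 + 12 = week 26 agrees with dating the questionnaires either 12 weeks after treatment or at 6 months. Against it, a compliance call at week 2 would come just as treatment begins, and the timeline's 12-week stop for laser is ambiguous. Even a settled start would not fix the origin. Section 1.0 dates the primary outcome from treatment, Section 3.0 dates questionnaires from end of treatment or from intake, and Section 3.0 dates photographs from the last treatment. As-needed steroid use means that the last treatment has no fixed date in that arm.

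**Contacts before 6 months.** Common to both arms: 2, of which 0 are described as asking about complications. Clinic sessions that could reveal a complication of earlier study treatment: laser 3 - 1 = 2, steroid 0. These are opportunities only; no text says that complications are recorded at laser sessions. If the 6-week point means week 6 from Day 0 and treatment starts at week 2, laser patients are in clinic that week and steroid patients have no scheduled contact.

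**Can the 6-month instruments recover early events?** Skindex looks back 4 weeks (Appendix 2), so at week 26 it reaches week 22. The VSQ looks back 1 week (Appendix 5), to week 25. Neither reaches week 20, the latest reading above. The symptom scale in Appendix 1 states no look-back period. No named questionnaire asks about infection, contact dermatitis or burn injury; the burning items record a symptom.

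**The case against.** The strongest reply is that the missing 6-week column is only a labelling matter. With a week-2 start, which the timeline's own arithmetic supports, the 8-week call falls exactly 6 weeks after first treatment, in both arms. The call description is a row label, not a script. Section 8.0 gives adverse event monitoring to study staff, and the coordinator who makes the calls could well ask. The case report forms may hold a common complications item, medical records are drawn on in both arms, and both arms are examined at 6 months and 1 year.

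Much of this stands. The 8-week call may be what was intended, and the forms are not shown. But the call serves only if the origin is first treatment. Section 1.0 dates its primary outcome from treatment, and on a post-treatment reading the point moves to about weeks 14 to 20, where no common contact exists. Section 8.0 supplies no common time or question, and Section 9.0 refers follow-up data back to the protocol's time-frame, which is the missing item. Records show what was reported and written down; later examinations show what is still present.

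A reader might go further in four ways that the documents do not support:

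- That complications are not monitored at all. Section 8.0 says that they are; what is lacking is a schedule and a method.
- That the laser arm must look worse because it is seen more often. No passage shows what is recorded at the sessions, so neither size nor direction can be claimed.
- That the origin is beyond inference. A week-2 start has real support; it is simply not stated or settled.
- That pain and dyspareunia are already covered by the questionnaires. These allow a comparison of symptoms at 6 months and 1 year, but the VSQ and Skindex windows are short, and the VSQ sexual-activity items are skipped by women who are not sexually active.

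**Conclusion.** The point holds as a gap between a stated outcome and the schedule meant to deliver it. The 6-week complications outcome has no stated origin, no timeline entry, and no early common contact assigned to it. As written, the early comparison may be missed or captured unequally.

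In size: 0 of 2 early common contacts are described as asking about complications, and only one reading of the 6-week point meets a common contact. The size and direction of any bias are not established. The primary comparison and the sample size are unaffected. The change should be made, but the main analysis does not hang on it.

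Confidence is high for the missing origin, row and column. It is lower for unequal capture, which depends on case report forms that are not shown. The week counts assume 6 months is week 26 from Day 0 and that treatment starts at Day 0 or week 2.

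**What to change.** - State in Section 1.0 the origin of the complication time points, and reconcile the treatment start between the timeline and the text.
- Have the coordinator ask one identical structured checklist of the Section 1.0 complications in both arms at the four existing common contacts: the 2- and 8-week calls and the 6-month and 1-year visits. Each should cover the whole period since the last contact, with dates of onset.
- If the stated origin is first treatment and treatment starts at week 2, name the 8-week call as the early time point. Otherwise, relabel the early time point to match an existing common contact.
- Add a complications row to the timeline.
- Compare the arms on answers from the common contacts. Report events found at laser sessions separately by source, without removing them.

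The cost is a few minutes at each contact, one extra safety table and some wording; no new visits or staff are needed. If treatment starts at week 2, the 2-week call may yield little post-treatment information.

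The fix leaves a later gap. The 8-week call falls in the week of the third laser session (Day 0 start) or before it (week-2 start). Complications after the call still rest on recall at 6 months: 26 - 8 = 18 weeks after the call, and 26 - 10 = 16 to 26 - 8 = 18 weeks after the third session.

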Lee A, 2015 ¹⁴	Case Series	Subjective symptom resolution	In women (N=5) with biopsy confirmed severe vulvar LS recalcitrant to topical corticosteroid treatment; four of whom responded positively to fractional CO2 laser treatment, and one to ablative CO2 laser therapy	Two patients needed repeat treatment at 6-8 months Two patients reported discomfort with laser treatment
Ratz L, 1984 ¹⁵	Case Report	Subjective symptom resolution and re-epithelization	One case of balanitis xerotica obliterans refractory to topical treatments resolved after CO2 laser treatment	Syncopal episode after treatment

Very little is known about long-term effects of CO2 fractional laser therapy use in the vulva or vagina, although the treatment is widely accepted in plastic and cosmetic surgery and dermatology. Increased marketing for laser vaginal rejuvenation has spawned a proprietary female genital cosmetic surgery industry in the US with very limited published outcome data. SmartXide⁸ –V2-LR has some established outcome data for treatment of genitourinary syndrome of menopause GSM, also known as vulvovaginal atrophy. Table 3 List outcomes of the SmartXide⁸ –V2-LR system for treatment of vaginal atrophy.

Table 3 Outcomes of SmartXide⁸ –V2-LR system for Vaginal Atrophy

Author and year	Trial Design	N	Primary Outcomes	Findings	Complications
Salvatore R, 2014 ⁸	Prospective	50	Objective vulvovaginal atrophy (VVA) symptoms- Vaginal Health Score Index (VHIS) Subjective VVA symptoms – 10 point visual analog scale	Fractional CO2 laser improved VVA all subjective symptoms in women; significant objective improvement VHIS (13.1+/- 2.5 at baseline vs. 23.1 +/- 1.9; p<0.001)	None

			(burning, vaginal itching, vaginal dryness, dyspareunia, and dysuria)		
SalvatoreR, 2015 ¹⁶	Prospective	77	-Sexual function and quality of life (Female sexual function index and Short form 12) -Subjective symptoms (vaginal burning, dryness, dyspareunia, and dysuria with visual analog scale)	-85% normal sexual life after CO2 laser therapy in not sexually active group -Significant improvement in FSFI and VAS scores after treatment -Significant improvement in overall satisfaction with sexual life after laser treatment	None

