3.0 STUDY DESIGN

Women presenting to the urogynecology clinic will be screened for lichen sclerosus. Vulvar biopsy will be performed for confirmation, and, if eligible, the patient will be consented to undergo baseline questionnaires, photodocumentation of vulvar lesions and randomization. Patient will be randomized to monthly LASER treatment for 3 months or topical STEROID therapy (temovate propionate .05% ointment nightly for one month, three times weekly for 2 additional months, then as needed) in a 1:1 ratio using a computer generated randomization schedule. Grouping assignments will be kept in sealed consecutively numbered, opaque envelopes. Because of the nature of the treatment, it will not be possible to blind patients but the assessor will be blinded to the intervention.

Patient questionnaires include multiple validated scales and surveys to provided reproducible measures of vulvar symptoms as primary and secondary outcomes. Questionnaires will be completed at the intake visit, repeated at 12 weeks after treatment is completed or 6 months from intake, and one year follow up. Subjective symptoms including vulvar itching, vulvar burning, vulvar irritation, pain with intercourse, tearing of the vulvar skin, painful urination, and painful defecation will be rated with a validated visual analog scale (VAS), scaled 0-10, see appendix 1. Higher values correspond to more bothersome symptoms. The Skindex-29 questionnaire is a subjective measure of skin symptoms validated against the Medical Outcomes Study 36-item Short-Form Survey (SF-36)¹⁷, appendix 2. The Skindex-29 was developed in dermatology and modified for use in vulvadynia¹⁸. The Skindex-29 is scored as a sum expressed on a 100-point scale with higher scores indicating lower quality of life. Validated quartiles are used to characterize disease symptoms, emotions, functioning, and overall score as either very little, mild, moderate, or severe¹⁹. Secondary outcomes of patient satisfaction and global impression of improvement will be collected using simple validated visual analog scale from 0-5, much worse to much better, appendix 4. A final subjective measure, the Vulvovaginal Symptoms Questionnaire (VSQ), a validated measure of vulvar symptoms, emotions, life impact, and sexual impact in postmenopausal women will be collected a secondary outcome²⁰, appendix 5. A higher total score on the VSQ corresponds to lower quality of life.

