Appendix 1:

Subjective Symptoms VISUAL ANALOG SCALE (VAS)

Not bothersome	Most Bothersome
0 1 2 3 4 5 6 7 8	9 10

SYMPTOMS

Vulvar itching
 Vulvar burning
 Vulvar irritation
 Pain with intercourse
 Tearing of vulvar skin
 Painful urination
 Painful defecation

Objective Signs VISUAL ANALOG SCALE (VAS)

Absent		Mild		Moderate		Severe				
0	1	2	3	4	5	6	7	8	9	10

SIGNS

- White plaques/hypopigmentation
- Cigarette paper, thin skin
- Introital narrowing
- Perianal involvement (figure of 8 shape)
- Loss of labia minora
- Fusion of labia minora
- Phimosis of clitoral hood
- Vulvar fissure
- Erosion

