11.	Embarrassment about your vulvar symptoms?	0  No 1  Yes
12.	The effects of your vulvar symptoms on your interactions with others?	0  No 1  Yes
13.	The effects of your vulvar symptoms on your desire to be with people?	0  No 1  Yes
14.	Your vulvar symptoms making it hard to show affection?	0  No 1  Yes
15.	The effects of your vulvar symptoms on your daily activities?	0  No 1  Yes
16.	Your vulvar symptoms affecting your desire to be intimate?	0  No 1  Yes
17.	Are you currently sexually active with a partner?	
	 No → Thank you. You are done with this questionnaire.	
	 Yes → Please proceed with the next 4 questions	
18.	The effects of your vulvar symptoms on your sexual relationships?	0  No 1  Yes
19.	Your vulvar symptoms causing pain during sexual activity?	0  No 1  Yes
20.	Your vulvar symptoms causing dryness during sexual activity?	0  No 1  Yes
21.	Your vulvar symptoms causing bleeding during sexual activity?	0  No 1  Yes

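### The symptom VAS rates pain with intercourse for every woman with no not-applicable option, so absence of pain and absence of intercourse cannot be told apart

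*Combined protocol and SAP*

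**What the plan says.** Section 1.0 defines the primary outcome as "subjective and objective cure of vulvar symptoms of itching, burning, dyspareunia at 12 weeks post treatment, or 6 months", using the Skindex-29 and the symptom VAS. A secondary outcome in the same section lists complications: "pain, infection, de novo or worsening dyspareunia, contact dermatitis and burns", at 6 weeks, 6 months and 1 year.

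Section 3.0 says that the symptoms, pain with intercourse among them, "will be rated with a validated visual analog scale (VAS), scaled 0-10", and that "Higher values correspond to more bothersome symptoms". Appendix 1 prints the item as one unconditional line, "Pain with intercourse". Its lower anchor, 0, means no bother. There is no not-applicable box and no preceding question on sexual activity.

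Section 4.0 requires symptomatic, biopsy-proven disease and post-menopausal status. It does not mention sexual activity. Section 12.0 gives no rule for scoring the VAS, for items that do not apply, or for classifying complications.

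The VSQ in Appendix 5 handles the same issue differently. Item 17 asks "Are you currently sexually active with a partner", and a woman who answers no skips the four sexual items that follow. Nothing applies that question to the VAS.

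**The concern.** Section 2.0 describes a disease that narrows the introitus and can make intercourse painful. Some eligible women will plausibly not be having intercourse, whether because of the disease or for other reasons. The VAS line has no correct answer for them, and women in the same state can be recorded in three different ways.

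At stake is one of the three symptoms named in the primary outcome, in a trial of 52 women. There is also a knock-on for safety. If baseline activity is not recorded alongside the complication, pain on resuming intercourse cannot be separated from pain that newly arises in a woman who was already active. Resumption is not a remote possibility: Table 3 in Section 2.0 reports "85% normal sexual life after CO2 laser therapy in not sexually active group" from an earlier vaginal atrophy study of this laser system.

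**Working it through.** **The plan's own figure.** The plan gives no figure for the VAS item or for the dyspareunia complication. Its one calculation (Section 5.0) concerns Skindex-29 change: difference 16, SD 22, one-sided alpha 0.05, 80% power. The normal approximation gives n = 2 × (1.645 + 0.842)² × 22² / 16² ≈ 23.4, so 24 per group, as stated; t-based power at 24 is 79.9%. The VAS does not enter this calculation. Recruiting 52 at 1:1 gives 26 per arm.

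**What one woman's record can look like.** Take a woman not having intercourse at baseline who resumes with a residual pain score of 4 (assumed):

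- baseline circled 0: change = 4 − 0 = +4, read as worsening;
- baseline left blank: change is missing;
- baseline scored 10, because pain is why she abstains: change = 4 − 10 = −6, read as improvement.

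If she resumes without pain after circling 0, the change is 0. Conversely, a woman who scored 4 at baseline, stops because of pain and then circles 0 has a change of −4 and reads as cured. Nothing in the documents says which entry is expected.

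**Size if every inactive woman circles 0.** These inputs are assumptions: q = share inactive at baseline, 0.2 to 0.6; r = share of those who resume, all with some pain, 0.1 to 0.5; p = residual score, 2 to 4.

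- Women per arm who could be misread = 26 × q × r. Low: 26 × 0.2 × 0.1 = 0.52. Middle: 26 × 0.4 × 0.25 = 2.6. High: 26 × 0.6 × 0.5 = 7.8.
- Artificial rise in the arm's mean item score = q × r × p. Low: 0.2 × 0.1 × 2 = 0.04. High: 0.6 × 0.5 × 4 = 1.2.

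If these women leave blanks, this shift is 0 and the problem is missing data instead.

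**Between-arm difference.** Assume 40% inactive (26 × 0.4 = 10.4 per arm), all circling 0, with half of those who resume reporting pain.

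- Laser, borrowing the 85% in Table 3: 10.4 × 0.85 × 0.5 = 4.4 women (17%).
- Steroid, assuming 30% resume: 10.4 × 0.30 × 0.5 = 1.6 women (6%).
- Steroid, using as a rough proxy the 77% complete symptom remission in the retrospective clobetasol series of 81 patients in Table 1: 10.4 × 0.77 × 0.5 = 4.0 women (15%).

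The gap is 2.9 women under one assumption (4.42 − 1.56) and 0.4 under the other. Remission is not resumption, so neither steroid figure is an estimate; the pair shows that the documents do not determine the gap.

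**The case against.** The strongest reply is that this is an unstated scoring rule, not a directional error. Much of that stands, and it rules out several stronger readings.

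- A reader might infer that the form makes an inactive woman score 0. It does not: the scale rates bother, so a blank or a high score is equally open to her.
- A reader might infer that a rise on the VAS is automatically counted as the dyspareunia complication. No section links the two. The complication has its own 6-week time point, while Section 3.0 schedules questionnaires only at intake, 6 months and one year. Section 8.0 lists painful intercourse among the laser risks and leaves adverse-event monitoring to staff and the investigator.
- A reader might infer a bias against the laser arm. That needs unequal resumption, and the only resumption figure comes from a vaginal atrophy study, not from this comparison.
- A reader might infer that the trial's power is affected. Section 5.0 powers Skindex-29 change, and the two-way ANOVA in Section 12.0 is on the Skindex-29 as well.

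Other instruments also capture avoidance in all women: Skindex items 11 and 29 (closeness and sex life) and VSQ item 16 (desire for intimacy).

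What remains is that none of these repairs the VAS line, which is part of the stated primary outcome. VSQ item 17 identifies women without a sexually active partnership, but it asks neither about intercourse itself nor for the reason. VSQ item 19, on pain during sexual activity, is skipped when a woman is inactive, so a first yes after resumption would also look new.

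**Conclusion.** The point holds as a defect in data collection. As printed, the VAS cannot separate a woman without pain from a woman without intercourse, and the plan has no rule to resolve it afterwards. Where inactive women circle 0, resuming with residual pain reads as worsening and stopping because of pain reads as cure.

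On the assumptions above, 0.5 to 7.8 women per arm of 26 could be affected, moving the mean item score by 0.04 to 1.2 points. These ranges rest on assumed shares and on every inactive woman circling 0. Neither the direction nor the size of a between-arm bias can be derived from the documents. The change should be made because a named primary symptom is affected and the remedy is nearly free. It does not threaten the powered Skindex-29 comparison.

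**What to change.** 1. Add to the VAS line a tick-box for not having intercourse, with two reasons: vulvar symptoms, or another reason. Code it as not applicable, never as 0.
2. Analyse VAS dyspareunia change in women having intercourse at baseline. Count those who stop because of vulvar symptoms as not improved. Selecting on baseline status avoids selecting on activity after treatment, which treatment may itself change.
3. Report resumption of intercourse by arm, with any pain on resumption, so that women who were avoiding intercourse at entry are not lost from view.
4. State how new or worsened dyspareunia is ascertained: source and threshold. Keep all women in this safety count and show it by baseline activity. Restricting the count to women active at baseline would hide painful intercourse, a listed laser risk, in women inactive at entry.

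The cost is one tick-box at each questionnaire visit and a smaller VAS dyspareunia comparison. If 20% to 60% are inactive at baseline (assumed), it would have 26 × 0.8 = 20.8 down to 26 × 0.4 = 10.4 women per arm before attrition.
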